11. STATISTICAL CONSIDERATIONS

The primary endpoint is the feasibility of PET/MRI for rectal cancer treatment response assessment and post-treatment surveillance for patients receiving chemoradiation as part of an NOM strategy. We are interested in the feasibility of PET/MRI for this indication to aid in the planning of a larger prospective trial of short-course radiation therapy followed by adjuvant chemotherapy for the NOM of rectal cancer patients, potentially using PET/MRI to assess for residual or recurrent disease following chemoradiation.

The primary endpoint, feasibility, will be analyzed using descriptive statistics, including exact 95% confidence intervals. Similarly, the secondary endpoint, changes in perceived disease status resulting from the addition to FDG-PET to MRI, will also be analyzed with descriptive statistics, including exact 95% confidence intervals.

A sample size of 20 patients, with an anticipated average of 3 scans/patient, will provide approximately 60 scans for feasibility assessment. If we observe a feasibility rate of 83.3% (i.e., 50 of 60 scans completed imaging sessions with adequate image quality), the exact 95% confidence interval for that proportion and sample size would be 72-92%. The lower limit of this confidence interval will effectively indicate that feasibility is $\geq 70\%$ and that the study has met its primary endpoint.

If a feasibility rate of 90% is observed for the first 20 scans after the optimization phase, the 95% confidence interval for that rate would be 68.3-98.8%. This lower bound will be deemed close enough to 70% to constitute success with respect to achieving the primary endpoint. Thus, enrollment of additional subjects could cease at this point (**early stopping**) at the discretion of the Principal Investigator. Notably, already enrolled subjects would continue receiving additional scans per protocol and will be included in the secondary endpoint analysis.

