7.2. PET protocol

For the first PET/MRI examination, the PET portion will begin at 55-65 minutes after administration of FDG according to the weight-based scale currently used for standard-of-care PET examinations. All patients will undergo a single bed position list-mode PET acquisition centered craniocaudally on the tumor. The acquisition will occur continuously throughout the MRI outlined above for an interval of at least 30 min. A total of 10 static PET image sets will be reconstructed from sequential 3 min frames (i.e., 0-3 min, 3-6 min, 6-9 min, etc.).

These 10 image sets will be assessed by the Principal Investigator for tumor motion throughout the 30 min PET acquisition. If the rectal cancer is deemed to be adequately stationary on review of the images from the first scan, the FDG will be reduced to one-fifth of the initial administered activity for the following scans, with a compensatory increase in the frame length to 15 min for reconstruction of static PET images. This modification will result in substantial dose reductions for subsequent imaging sessions but should not compromise image quality.

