10. IMAGE AND DATA ANALYSIS

10.1. Primary objective

The primary objective is to determine technical feasibility of PET/MRI for rectal cancer treatment response assessment and post-treatment surveillance for patients receiving chemoradiation as part of a NOM strategy. Technical feasibility (**the primary endpoint**) will be defined as completion of the PET/MRI rectal cancer protocol with acceptable image quality in $\geq 70\%$ of scans. This proportion is based on a predicted success rate, informed by prior experience with PET/MRI studies. For patients imaged at multiple time points after enrollment (see 7), all available PET/MRIs will be included in the feasibility analysis. Patients able to remain on the scanner for the full duration of the planned data acquisition without any serious adverse events (see 8.1.2) will be considered to have *completed* the PET/MRI rectal cancer protocol. Image quality will be assessed by the Principal Investigator on review at a dedicated workstation with specialized PET/MR software. A standardized Likert-based scoring scheme will be

utilized to capture subjective assessments of image contrast (1 = worst; 5 = best), image resolution (1 = worst; 5 = best), and image artifact ‘freeness’ (1 = worst; 5 = best). Image sets scoring ≥ 3 in all three categories will be considered of *acceptable quality*.

The first imaging session for the first two subjects enrolled will occur with the Principal Investigator present in the scanner control room to direct the tweaking of acquisition parameters and imaging planes in real time. If the Principal Investigator is satisfied with the quality of the reconstructed PET and MR images from these first two cases, as viewed on a dedicated workstation with specialized PET/MR software, the imaging protocol will be considered optimized, and the relevant acquisition parameters will be ‘locked’ as the default for subsequent imaging sessions for these two patients and for all other enrolled subjects. The Principal Investigator will review each of the remaining cases after it is finished (i.e., not in real time but soon after completion) to simulate conditions under which PET/MRI examinations are typically performed (i.e., technologist operating scanner without radiologist present), making an assessment of image quality at that time according to a predetermined qualitative scale.

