10.2. Secondary objective

The secondary objective is to estimate the added value of PET/MRI relative to MRI only for detecting residual or recurrent rectal cancer following chemoradiation in patients on a NOM protocol. The MRI component of the PET/MRI will be performed as a standard-of-care examination, with the formal study interpretation flowing to the subject’s medical record and replacing the interpretation that would normally be provided by the clinical reading room. These interpretations will include descriptions of local tumor extension (T-stage) and locoregional lymph node involvement (N-stage). Any potential sites of metastatic disease (M-stage) will also be described, though assessment will be limited to the pelvis. For post-treatment imaging studies, an mrTRG will also be provided according to a standardized scale.

Then, the same study reader interpreting the MRI (initially blinded to the PET data) will qualitatively and quantitatively (e.g., post-treatment SUV_{max}) assess the reconstructed PET images (with and without MRI fusion). This reader will then render a PET/MRI tumor regression grade (pmrTRG) based on the PET and MRI data, using a standardized scoring system. Changes in the perceived disease status (i.e., mrTRG vs. pmrTRG; **the secondary endpoint**) will be recorded. This study interpretation will also flow to the patient’s clinical chart via a separate report. The patient’s multidisciplinary care team will consider the pmrTRG in conjunction with results of other available data (e.g., lower endoscopy and DRE) and make a decision whether to categorize the case as cCR.

Subjects deemed to have anything other than cCR will be evaluated for surgical management (TME or endoscopic resection). In contrast, subjects deemed to have a cCR will continue on the NOM surveillance protocol, with repeat PET/MRIs at regular intervals as indicated in the Schema (also see 7). These subsequent PET/MRIs will be analyzed as outlined in the preceding two paragraphs. Thus, the secondary endpoint will consider all scans that each patient undergoes, rather than just the first scan (as outlined in 10.1 for the primary endpoint). Pathology and clinical follow-up

data will be collected for up to 5 years after enrollment of the patient in the study for correlation with the PET/MRI findings.

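### The 72-92% feasibility interval treats about 60 repeat scans from 20 patients as independent, so its lower limit cannot be relied on to show 70%

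*Combined protocol and SAP*

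**What the plan says.** Section 11 sets the denominator: "A sample size of 20 patients, with an anticipated average of 3 scans/patient, will provide approximately 60 scans for feasibility assessment". The primary endpoint "will be analyzed using descriptive statistics, including exact 95% confidence intervals". For 50 successes in 60 scans (83.3%), "the exact 95% confidence interval for that proportion and sample size would be 72-92" per cent. The plan then draws its conclusion from that figure: "The lower limit of this confidence interval will effectively indicate that feasibility is" at least 70%, and the primary endpoint is met. The secondary endpoint "will also be analyzed with descriptive statistics, including exact 95% confidence intervals".

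Section 10.1 confirms that repeat scans are pooled: "all available PET/MRIs will be included in the feasibility analysis". Section 7 schedules up to 6 imaging sessions per patient. Section 10.2 points the other way. It says the secondary endpoint considers every scan "rather than just the first scan (as outlined in 10.1 for the primary endpoint").

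No section mentions within-patient correlation, a design effect, or a patient-level analysis.

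**The concern.** An exact binomial interval assumes independent observations. Here the observations are repeat scans of the same 20 people. A scan succeeds if the patient stays on the scanner for the full acquisition without a serious adverse event and the images score at least 3 for contrast, resolution and freedom from artifact. Tolerance of the scanner, motion and sources of artifact are partly patient traits. Section 7.2 adds a possible link between a patient's scans: "If the rectal cancer is deemed to be adequately stationary on review of the images from the first scan", that patient's later scans are acquired differently. Positive correlation is therefore plausible, and it would make the interval too narrow.

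This matters because Section 11 uses the lower limit to declare the primary endpoint met and intends the result to inform a larger trial. The same 50/60 could support or fail to support the 70% claim depending on whether the 10 failures are spread over many patients or concentrated in a few. The plan would report 72-92% in every case.

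**Working it through.** **Inputs.** From Section 11: 20 patients, an average of 3 scans, 60 scans, 50 successes, two-sided exact 95% interval, 70% threshold. From Section 7: at most 6 scans per patient. The ICC is not in the documents and is varied as an assumption.

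**1. Reproduce the plan's figure.** The Clopper-Pearson limits for x successes in n are the 2.5% quantile of Beta(x, n−x+1) and the 97.5% quantile of Beta(x+1, n−x). For 50/60 these are 71.48% and 91.71%, which agrees with 72-92% apart from rounding of the lower limit. The early-stopping interval for 18/20 reproduces exactly (68.3-98.8%). The stated interval is thus the one for 60 independent scans.

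**2. Slack.** For 49/60 the lower limit is 69.6%, so 50/60 is the smallest count that reaches 70%.

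**3. Allow for clustering.** With m scans per patient, effective n = 20m / [1 + (m−1) × ICC]. For m = 3 and ICC 0.2 this is 60/1.4 = 42.9. Clopper-Pearson at 83.3% and the effective n gives:

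| Assumed ICC | Effective n | 95% interval |
|---|---|---|
| 0 | 60.0 | 71.5-91.7% |
| 0.1 | 50.0 | 70.1-92.4% |
| 0.2 | 42.9 | 68.8-92.9% |
| 0.3 | 37.5 | 67.6-93.5% |
| 0.5 | 30.0 | 65.3-94.4% |

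The lower limit crosses 70% at ICC 0.108. It crosses 68.3%, the bound the plan tolerates at its early look, at ICC 0.241.

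**4. Same 50/60, ICC estimated from the data.** This uses the ANOVA estimate, ICC = (MSB − MSW) / [MSB + (m−1) × MSW], set to 0 if negative. For five patients failing twice each, MSB = 0.263 and MSW = 0.083, so ICC = (0.263 − 0.083)/(0.263 + 2 × 0.083) = 0.42 and effective n = 60/1.84 = 32.7.

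| How the 10 failures fall | Estimated ICC | Lower limit |
|---|---|---|
| 10 patients, 1 each | 0 (truncated) | 71.5% |
| 8 patients (2, 2, six 1s) | 0.06 | 70.7% |
| 7 patients (2, 2, 2, four 1s) | 0.18 | 69.1% |
| 5 patients, 2 each | 0.42 | 66.2% |
| 4 patients (3, 3, 3, 1) | 0.89 | 61.3% |

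**5. Operating characteristics of the plan's interval** (beta-binomial model, 20 patients × 3 scans). False success means reaching at least 50/60 when the true rate is 70%.

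| ICC | Coverage at true 83.3% | False success |
|---|---|---|
| 0 | 96% | 1.4% |
| 0.1 | 94% | 2.2% |
| 0.2 | 92% | 3.1% |
| 0.3 | 90% | 4.1% |
| 0.5 | 86% | 6.2% |

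With unequal counts (1 to 6 scans, total 60), coverage at ICC 0.2, 0.3 and 0.5 is 90%, 87% and 80%, and false success is 4.2%, 5.7% and 8.6%. With all 6 scans for every patient, coverage is 86%, 81% and 73%, and false success is 6.5%, 8.9% and 13.1%. In that case the 83.3% example itself (100/120) stays above 70% up to an ICC of about 0.29.

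**6. First-scan reading.** If only first scans count there is no clustering, but n is 20. Then 17/20 has a lower limit of 62.1%, 18/20 gives 68.3%, and 19/20 (75.1%) is the first count to reach 70%. The 60-scan interval does not apply.

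**The case against.** The strongest reply is that the size of the effect is assumed. No ICC is documented, and below about 0.11 the worked example still passes. The 50/60 count is an illustration that sits on the edge: 51/60 moves the break-even ICC to 0.26, 52/60 to 0.44 and 54/60 to 0.83. Section 5.2 excludes claustrophobia, tremor and artifact-producing implants, which removes some of the likeliest persistent causes. The dose-reduction step in Section 7.2 is a weak mechanism, since the plan expects no loss of image quality. At an average of 3 scans the inflation of false success is modest for a single-centre pilot, and 6 scans per patient is the ceiling, not the expectation. All of this stands, and it limits the size of the problem. It does not justify assuming an ICC of zero.

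Two further points carry less weight. Section 10.1 states the criterion as a proportion of scans with no confidence limit, and Section 11 calls the analysis descriptive; but Section 11 does use the lower limit to declare success. The parenthesis in Section 10.2 could be attached to the all-scans clause, which would remove the conflict with Section 10.1. Its nearest reading does conflict, and the wording needs repair either way.

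On the remedy, an ICC estimated from about 10 failures is noisy. With truly independent scans, about 15% of datasets with exactly 50/60 would fall below 70% through estimation error alone. That is a real cost, though overall the chance of success at a true 83.3% falls only from about 58% to 56%.

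**Conclusion.** The concern holds. The stated interval assumes independent scans, the design does not supply them, and the plan rests its primary conclusion on the resulting lower limit. The direction of the error depends on positive within-patient correlation, which is plausible but unmeasured. With 3 scans per patient, the lower limit for 50/60 runs from 71.5% at ICC 0 to 65.3% at ICC 0.5, and the 70% claim is lost above about 0.11. Unequal scan counts make the undercoverage worse. The secondary endpoint has the same weakness, and so may the early look, because the first 20 scans can include repeats. The conflict over the unit of analysis needs resolving whatever the ICC. This should be fixed, but it does not invalidate the study.

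**What to change.** 1. Reconcile Section 10.2 with Sections 10.1 and 11, and state once whether the primary endpoint uses all scans or first scans only.
2. If all scans count, replace the scan-level exact interval for both endpoints with Clopper-Pearson at the effective sample size N / [1 + (Σmᵢ²/N − 1) × ICC]. Here mᵢ is the number of scans for patient i, N is their total, and the ICC is the ANOVA estimate truncated at 0. Set it to 0 if every scan has the same outcome, where the estimate is undefined. Base the 70% reading in Section 11 on this interval. In simulation over ICC 0 to 0.5, with 3 or 6 scans per patient, it kept coverage at about 94-97% and false success at about 1-3%. A patient-level percentile bootstrap is not a good substitute: with 20 patients × 3 scans and a true rate of 70%, its false success was 5.9%, 5.2% and 5.9% at ICC 0, 0.1 and 0.3.
3. Restate the 72-92% example over a range of ICCs, with 71.5% as the unadjusted lower limit.
4. Report the first-scan or per-patient feasibility rate as a sensitivity analysis.

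The cost is SAP wording and a few lines of code. The interval is wider when failures cluster, and the ICC estimate is imprecise. No extra patients or scans are needed.

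### After early stopping, Section 11 does not say whether later scans update the primary feasibility result, and Sections 10.1, 10.2 and 11 imply different primary analysis sets

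*Combined protocol and SAP*

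**What the plan says.** Section 10.1 defines the primary endpoint as "completion of the PET/MRI rectal cancer protocol with acceptable image quality in" at least 70% of scans. For patients imaged more than once it says that "all available PET/MRIs will be included in the feasibility analysis", with no exception for early stopping. It also describes an optimization phase, the first session of each of the first two subjects.

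Section 10.2 says that the secondary endpoint covers every scan a patient has, "rather than just the first scan (as outlined in 10.1 for the primary endpoint". Section 10.1 contains no such restriction.

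Section 11 plans on many scans per patient: "A sample size of 20 patients, with an anticipated average of 3 scans/patient, will provide approximately 60 scans for feasibility assessment". The early-stopping paragraph begins "If a feasibility rate of 90% is observed for the first 20 scans after the optimization phase". It accepts the resulting lower confidence limit, 68.3%, as near enough to 70% to count as success on the primary endpoint, and allows enrolment to end at the Principal Investigator's discretion. It closes by noting that "already enrolled subjects would continue receiving additional scans per protocol and will be included in the secondary endpoint analysis". The primary analysis is not mentioned in that sentence.

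**The concern.** The three sections point to different primary analysis sets once the trial stops early: all scans (10.1), first scans (10.2), or the 20 scans on which success was declared (one reading of 11). Scans after the stop are still performed and, under 10.1, still scored by the Principal Investigator. The plan does not say whether they can change the feasibility conclusion, or what is concluded if the 20-scan and all-scan results differ.

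The feasibility figure is meant to inform a larger trial, so it matters which one is carried forward. Later scans may also differ from early ones. Under Section 7.2, scans after a subject's first may use one-fifth of the FDG activity with longer frames. The plan expects image quality to hold, but image quality is part of the primary endpoint. A favourable run in the first 20 scans should be open to correction by the trial's own later data.

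**Working it through.** **Inputs.** From Section 11: 18/20 at the early look, 50/60 in the full sample, an average of 3 scans per patient, exact 95% intervals. From Section 7: up to 6 scans per patient, about one every 6 months in surveillance, target accrual of 10 patients per year. From 10.1: a 70% threshold and two optimization sessions.

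**1. The plan's own figures.** The exact (Clopper-Pearson) limits for x successes in n scans are the 2.5% quantile of Beta(x, n-x+1) and the 97.5% quantile of Beta(x+1, n-x).
- 18/20: 68.3-98.8%, as stated.
- 50/60: 71.5-91.7%, against the plan's 72-92%; this agrees within rounding.

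**2. Scans still to come at the stop (assumptions).** Take even accrual, one patient every 1.2 months, with sessions 6 months apart and the two optimization sessions set aside. The 20th scan then falls at about month 14.4 from the first enrolment, in a three-way tie: subject 13's first session, subject 8's second and subject 3's third. So 12 or 13 subjects are enrolled. Using 12:
- 3 scans per patient: 12 x 3 - 2 = 34 in total, 14 after the stop.
- 6 scans per patient: 12 x 6 - 2 = 70 in total, 50 after the stop.

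With 13 subjects, 17 and 56 scans follow. Section 12 sets no time restriction on scans, so this timeline is illustrative.

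**3. Pooled result after 18/20.**

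| Later success | Later scans | Pooled | Exact 95% CI |
|---|---|---|---|
| 70% | about 10 of 14 | 28/34 = 82.4% | 65.5-93.2% |
| 70% | 35 of 50 | 53/70 = 75.7% | 64.0-85.2% |
| 90% | 45 of 50 | 63/70 = 90.0% | 80.5-95.9% |

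In the last row the interval is 95.9 - 80.5 = 15.4 points wide, against 98.8 - 68.3 = 30.5 at the early look: about half.

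**4. Chance that the pooled lower limit falls below 70%.** Let m be the smallest count in N scans whose exact lower limit is at least 70%: m = 30 for N = 34, and m = 50 for N = 60 (the planned total, which is likely too many if enrolment stops). With k = N - 20 later scans, the chance is P(Binomial(k, p) < m - 18).

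| Later scans k | Successes needed (m - 18) | p = 70% | p = 80% |
|---|---|---|---|
| 14 | 12 | 84% | 55% |
| 40 | 32 | 89% | 41% |

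**5. The 10.2 parenthesis against Section 11.** One scan per patient gives at most 20 scans from 20 patients, or 20 - 2 = 18 once the optimization sessions are set aside. Neither the 60-scan calculation nor a look at 20 post-optimization scans can be met that way. The parenthesis thus conflicts with Section 11 as well as with 10.1.

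All these calculations treat scans as independent. At up to 6 scans per patient, 20 scans could come from as few as 4 patients (20/6 = 3.3), so the intervals may be too narrow.

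**The case against.** The strongest reply is that there is no conflict. Section 11 includes continuing subjects in the secondary analysis; it does not remove them from the primary one. Section 10.1 covers all scans without exception, and only enrolment stops. Read together, 10.1 already governs. This is also a descriptive single-arm pilot in which stopping is optional.

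Much of that stands, and it rules out some stronger readings that a reader might infer:
- *Later scans are kept only for the secondary endpoint, and the primary result is frozen at 20 scans.* Section 11 says neither. Nor does it say that 90% will be the figure reported.
- *Most of the feasibility data would be lost.* At the plan's average of 3 scans per patient, the scans after the stop are 14 of 34, or 41%. They are a majority only nearer the 6-scan ceiling.
- *The first 20 scans leave out nearly all later surveillance.* Enrollment point #3 subjects enter during surveillance, so a first study scan can be a late surveillance scan. The mix of enrollment points is not given.
- *Later scans would overturn the endpoint.* With 70% later success, a rate assumed here and not taken from the documents, both pooled estimates stay above 70%. Only the lower-limit criterion used in Section 11 is missed.

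The reply does not remove the gap. Section 11 declares success on 20 scans and names one analysis for what follows; 10.2 contradicts 10.1 outright; and no rule says which result prevails.

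**Conclusion.** The concern holds as an unresolved conflict over the primary analysis set, not as a demonstrated exclusion of data. If enrolment stops early, success declared on 18/20 can sit beside an all-scan result whose lower limit is below 70%. If later scans truly succeed 70% of the time, the chance of that is 84% with 14 further scans and 89% with 40. If they succeed 80% of the time it is 55% and 41%. If later scans hold at 90%, using them strengthens the claim. These sizes rest on independent scans, exactly 18/20 at the look, and assumed scan totals; the 14 also assumes about 12 subjects enrolled at the stop. The need to reconcile the three sections does not depend on any of these assumptions, and it should be met before analysis.

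**What to change.** In Section 11, replace the closing sentence on early stopping with text to this effect: *Early stopping closes enrolment only. The 20-scan result is interim and supports only the decision to stop enrolment. Enrolled subjects continue scans per protocol. The final primary estimate, its interval and the conclusion on feasibility use all available scans per 10.1, including those after the stop; the same subjects also enter the secondary analysis.* Amend the preceding wording that treats the 20-scan result as achieving the primary endpoint, so that the two agree.

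State whether the two optimization scans count in the final denominator; in the illustration this is 34 or 36 scans, and 70 or 72. Correct the parenthesis in 10.2 so that it no longer describes the primary endpoint as using the first scan.

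The cost is a few sentences. The scans and their scoring are already planned, so no patient has an extra procedure. The downside is that the primary result is final only when the follow-up scans finish, and it may be less favourable than at the 20-scan look.
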